**<each group>:**

- RSV-Ld = Low dose ChAd155-RSV vaccine (5 x 10^9 vp)
- RSV-Md = Middle dose ChAd155-RSV vaccine (1.5 x 10^10 vp)
- RSV-Hd = High dose ChAd155-RSV vaccine (5 x 10^10 vp)
- Placebo-Ld = Non-active control (0.5 ml)
- Placebo-Md = Non-active control (0.15 ml)
- Placebo-Hd = Non-active control (0.5 ml)
- N = total number of subjects
- n/% = number / percentage of subjects in a given category
- Value = value of the considered parameter
- N with data = number of subjects with documentation of the corresponding data
- SD = standard deviation

**Template 6 Summary of vital signs characteristics <Exposed set>**

			<each group> N =	Total N =
Visit	Characteristics	Parameters	Value	Value
<Each visit>	Height (Cm)	N with data		
		Mean		
		SD		
		Median		
		Minimum		
		Maximum		
	Weight (Kg)	N with data		
		Mean		
		SD		
		Median		
		Minimum		
		Maximum		
	Heart rate (Beats per minute)	N with data		
		Mean		
		SD		
		Median		
		Minimum		
		Maximum		
	Respiratory rate (Breath per minute)	N with data		
		Mean		
		SD		
		Median		
		Minimum		
		Maximum		
Temperature/(Axillary) (°C)	N with data			
	Mean			
	SD			
	Median			
	Minimum			
	Maximum			

**<each group>:**

RSV-Ld = Low dose ChAd155-RSV vaccine ( $5 \times 10^9$  vp)  
 RSV-Md = Middle dose ChAd155-RSV vaccine ( $1.5 \times 10^{10}$  vp)  
 RSV-Hd = High dose ChAd155-RSV vaccine ( $5 \times 10^{10}$  vp)  
 Placebo-Ld = Non-active control (0.5 ml)  
 Placebo-Md = Non-active control (0.15 ml)  
 Placebo-Hd = Non-active control (0.5 ml)  
 N = total number of subjects  
 N with data = number of subjects with documentation of the corresponding data  
 Value = value of the considered parameter  
 SD = standard deviation

**Template 7 Distribution of weight for age Z-score (WAZ) at vaccination  
<Exposed Set>**

Visit	Characteristics	Each group N =		Total N =	
		n	%	n	%
Day 1	Normal (-1 < WAZ < 0)				
	Mildly underweight (-2<WAZ<-1)				
	Moderately underweight (-3<WAZ<-2)				
	Severely underweight (WAZ<-3)				
Day 366	Normal (-1 < WAZ < 0)				
	Mildly underweight (-2<WAZ<-1)				
	Moderately underweight (-3<WAZ<-2)				
	Severely underweight (WAZ<-3)				

<group>

RSV-Ld = Low dose ChAd155-RSV vaccine (5 x 10^9 vp)  
 RSV-Md = Middle dose ChAd155-RSV vaccine (1.5 x 10^10 vp)  
 RSV-Hd = High dose ChAd155-RSV vaccine (5 x 10^10 vp)  
 Placebo-Ld = Non-active control (0.5 ml)  
 Placebo-Md = Non-active control (0.15 ml)  
 Placebo-Hd = Non-active control (0.5 ml)

N = Total number of subjects

n = number of subjects in each category

% = n / Number of subjects with available results x 100

For weight for age Z score calculation of each subject, median = XX and SD = YY

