### 11.3.3. Demography

- Age: Age at the reference activity, computed as the number of units between the date of birth and the reference activity. Note that due to incomplete date, the derived age may be incorrect by 1 month when month is missing from the birthdate. This may lead to apparent inconsistency between the derived age and the eligibility criteria/the age category used for randomization.
- Conversion of weight to kg: The following conversion rule is used:  
$$\text{Weight in Kilogramm} = \text{weight in Pounds} / 2.2$$
$$\text{Weight in Kilogramm} = \text{weight in oncs} / 35.27$$

The result is rounded to 2 decimals.
- Conversion of height to cm: The following conversion rule is used:  
$$\text{Height in Centimetres} = \text{Height in Feet} * 30.48$$
$$\text{Height in Centimetres} = \text{Height in Inch} * 2.54$$

The result is rounded to the unit (ie no decimal).
- Conversion of temperature to °C: The following conversion rule is used:  
$$\text{Temperature in } ^\circ\text{Celsius} = ((\text{Temperature in } ^\circ\text{Fahrenheit} - 32) * 5) / 9$$

The result is rounded to 1 decimal.

- Calculation of weight for age Z-score (WAZ) for each subject (rounded to 2 decimal):

$$WAZ = (\text{Weight of subject} - \text{median weight}) / \text{Standard deviation for weight}$$

- Calculation of height for age Z-score (HAZ) for each subject (rounded to 2 decimal):

$$HAZ = (\text{Height of subject} - \text{median height}) / \text{Standard deviation for height}$$

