**Template 8 Distribution of height for age Z-score (HAZ) at vaccination <Exposed Set>**

Visit	Characteristics	Each group N =		Total N =	
		n	%	n	%
Day 1	Normal (-1 < HAZ < 0 )				
	Mildly stunted (-2<HAZ<-1)				
	Moderately stunted (-3<HAZ<-2)				
	Severely stunted (HAZ<-3)				
Day 366	Normal (-1 < HAZ < 0 )				
	Mildly stunted (-2<HAZ<-1)				
	Moderately stunted (-3<HAZ<-2)				
	Severely stunted (HAZ<-3)				

<group>

RSV-Ld = Low dose ChAd155-RSV vaccine (5 x 10^9 vp)  
 RSV-Md = Middle dose ChAd155-RSV vaccine (1.5 x 10^10 vp)  
 RSV-Hd = High dose ChAd155-RSV vaccine (5 x 10^10 vp)  
 Placebo-Ld = Non-active control (0.5 ml)  
 Placebo-Md = Non-active control (0.15 ml)  
 Placebo-Hd = Non-active control (0.5 ml)

N = Total number of subjects

n = number of subjects in each category

% = n / Number of subjects with available results x 100

For height for age Z score calculation of each subject, median = XX and SD = YY

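### The weight- and height-for-age tables have no category for a Z-score of 0 or more, so infants at or above the reference median are unclassified and the Normal row is understated

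*SAP*

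**What the plan says.** SAP Section 6.1.1 plans weight-for-age (WAZ) and height- or length-for-age (HAZ) Z-scores on the Exposed Set at first vaccination, Day 366 and Day 731. Section 11.3.3 derives each score as the subject's value minus a median, divided by a standard deviation, rounded to two decimals. It does not say which reference supplies the median and SD.

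Section 13.2 gives the displays. In Template 7 the rows for Day 1 and Day 366 are "Normal (-1 < WAZ < 0", then "Mildly underweight (-2<WAZ<-1", then a moderate row from -3 to -2 and a severe row below -3. Template 8 repeats this for height, beginning with "Normal (-1 < HAZ < 0". Every limit is a strict inequality. The percentage is defined as "n / Number of subjects with available results x 100". The footnotes carry placeholders: "For weight for age Z score calculation of each subject, median = XX and SD = YY" for weight and "For height for age Z score calculation of each subject, median = XX and SD = YY" for height.

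**The concern.** A table of nutritional status should place every child with a result in exactly one row. Here the top row stops at zero. Since Z is zero at the reference median, a child of exactly median or greater weight or height has no row. The denominator still counts that child, so the percentages fall short of 100% and the Normal row covers only children between one SD below the median and the median.

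The Normal row would therefore show about a third of infants where most belong. A reader of the study report could take this as a poorly nourished sample or as heavy missing data, when neither is the case.

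**Working it through.** The plan states no figure for these tables, so there is nothing to reproduce first.

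**Inputs.**
- Row limits and denominator: SAP 13.2, Templates 7 and 8.
- Z = (value - median)/SD, rounded to two decimals: SAP 11.3.3.
- Exclusion of infants below the fifth percentile of the local weight-for-age curve: Protocol 5.3.
- Sample size, at least 64 with two doses and up to 96 enrolled: Protocol 5.1 and the SAP Table 1 footnote.
- Assumption, not in the documents: Z is normal with SD 1 and mean m relative to the reference. Φ is the standard normal distribution function.

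**Step 1. The gap.** Z ≥ 0 holds exactly when the value is at or above the median. No row in either template includes such values, and no other SAP text adds one.

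**Step 2. Standard normal, m = 0.**
- Normal: Φ(0) - Φ(-1) = 34.1%
- Mild: Φ(-1) - Φ(-2) = 13.6%
- Moderate: Φ(-2) - Φ(-3) = 2.1%
- Severe: Φ(-3) = 0.1%
- Unclassified: 1 - Φ(0) = 50.0%, which is 32 of 64 or 48 of 96 infants

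**Step 3. Day 1 weight with the eligibility limit.** If the local curve matches the Z-score reference, entry weights are cut off at Z = -1.645 and each share is divided by 0.95.
- Unclassified: 0.50/0.95 = 52.6%, about 34 of 64 or 51 of 96
- Normal: 0.341/0.95 = 35.9%
- Mild: (0.159 - 0.05)/0.95 = 11.4%
- Moderate and severe: essentially empty

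This step does not carry over to height or to Day 366.

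**Step 4. Sensitivity to the mean.** Unclassified share = 1 - Φ(-m), or [1 - Φ(-m)]/[1 - Φ(-1.645 - m)] with the weight cut-off.

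| Assumed mean Z | No cut-off | With cut-off |
|---|---|---|
| -0.5 | 30.9% | 35.3% |
| 0 | 50.0% | 52.6% |
| +0.5 | 69.1% | 70.3% |

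**Step 5. Exact boundary values.** Scores of exactly -1, -2 or -3 also have no row. With rounding to two decimals, the chance of exactly -1.00 under a standard normal is about 0.242 × 0.01 = 0.24%, or 96 × 0.0024 = 0.23 of an infant. This is trivial.

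**Step 6. After correction.** With Normal defined as Z ≥ -1, its share at m = 0 becomes 1 - Φ(-1) = 84.1% instead of 34.1%. With the Day 1 weight cut-off it becomes 88.6% instead of 35.9%. The rows then cover every value and sum to 100%.

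**The case against.** The strongest reply is that these are mock tables. The introduction to SAP Section 13 says that displays, titles and footnotes are illustrative, and that minor changes need no SAP amendment. A programmer may well notice the gap. The rows that identify undernutrition are counted correctly apart from ties, their percentages use the right denominator, and the missing share can be found by subtraction. Protocol 11.7 asks only for descriptive weight and height, which Template 6 supplies in full. All of this stands and keeps the point small. It does not remove the gap: the same limits appear at both visits in both templates, and no text states other cut-offs.

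Two stronger readings are tempting. First, a reader might infer from the footnotes and the formula without age or sex terms that one median and SD will serve all infants aged 12 to 23 months, so that older infants look better nourished through age alone. The documents do not support that. XX and YY are unfilled placeholders in footnotes declared illustrative, and the SAP calls the quantity a for-age score throughout. Protocol 1.2.4.3 also already uses an age- and sex-specific weight percentile. What the text does show is that the reference is not named.

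Second, a reader might conclude that the growth tables are wrong for most infants. The unclassified share depends on an assumed distribution and is below half at the lower end of the range. For the unclassified infants, the fault is a missing row rather than a false underweight or stunting label.

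**Conclusion.** The point holds in a limited form. As written, Templates 7 and 8 leave infants at or above the reference median without a category and understate the Normal row. The gap itself follows from the text alone. Its size is about half of infants under an assumed standard normal and about 53% for Day 1 weight if the local curve matches the reference. It is roughly 31% to 70% for an assumed mean Z of -0.5 to +0.5. The missing name of the reference in Section 11.3.3 is a secondary matter of clarification, not evidence of a wrong calculation. The tables are descriptive and feed no endpoint, so this is a desirable correction rather than a necessary one.

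**What to change.** In Templates 7 and 8, set the rows to Normal Z ≥ -1, mild ≥ -2 to < -1, moderate ≥ -3 to < -2, and severe < -3. Add a separate upper category if one is wanted.

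In Section 11.3.3, add a sentence naming the reference standard and stating that the median and SD are specific to age and sex. The standard must cover both sexes, weight, and length or height, since Protocol 6.6.6 changes from length to height at 24 months. It must also reach the later visits: Protocol Table 5 puts Day 365 at 24-35 months and Day 730 at 36-47 months. The WHO chart in the protocol's reference list appears from its file name to be girls' weight from 0 to 2 years, so it would not be enough alone.

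The cost is a template edit, which Section 13 allows without an amendment, plus one sentence and a reference table for the programmer. No data collection changes.

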**Template 8 Distribution of height for age Z-score (HAZ) at vaccination <Exposed Set>**

Visit	Characteristics	Each group N =		Total N =	
		n	%	n	%
Day 1	Normal (-1 < HAZ < 0 )				
	Mildly stunted (-2<HAZ<-1)				
	Moderately stunted (-3<HAZ<-2)				
	Severely stunted (HAZ<-3)				
Day 366	Normal (-1 < HAZ < 0 )				
	Mildly stunted (-2<HAZ<-1)				
	Moderately stunted (-3<HAZ<-2)				
	Severely stunted (HAZ<-3)				

<group>

RSV-Ld = Low dose ChAd155-RSV vaccine (5 x 10^9 vp)  
 RSV-Md = Middle dose ChAd155-RSV vaccine (1.5 x 10^10 vp)  
 RSV-Hd = High dose ChAd155-RSV vaccine (5 x 10^10 vp)  
 Placebo-Ld = Non-active control (0.5 ml)  
 Placebo-Md = Non-active control (0.15 ml)  
 Placebo-Hd = Non-active control (0.5 ml)

N = Total number of subjects

n = number of subjects in each category

% = n / Number of subjects with available results x 100

For height for age Z score calculation of each subject, median = XX and SD = YY

**Template 9 Deviations from specifications for age and intervals between study visits up to Day X <Exposed Set>**

	Age	SCR-Dose:1	Dose:1-VISIT3 (D4)	Dose:1-VISIT4 (D8)	Dose:1-Dose:2	Dose:2-VISIT7 (D34)	Dose:2-VISIT8 (D38)	Dose:2-VISIT9 (D61)	Dose:1-VISIT10 (D366)	Dose:1-VISIT11 (D731)
Group	Protocol	Protocol	Protocol	Protocol	Protocol	Protocol	Protocol	Protocol	Protocol	Protocol
	from 12 to 23 months	from 1 to 30 days	from 3 to 4 days	from 7 to 10 days	from 23 to 36 days	from 3 to 4 days	from 7 to 10 days	from 28 to 35 days	from 335 to 395 days	from 700 to 760 days
<each group>	N									
	n									
	%									
	range									

**<each group (pooled groups)>:**

RSV-Ld = Low dose ChAd155-RSV vaccine (5 x 10^9 vp)  
 RSV-Md = Middle dose ChAd155-RSV vaccine (1.5 x 10^10 vp)  
 RSV-Hd = High dose ChAd155-RSV vaccine (5 x 10^10 vp)  
 Placebo-Ld = Non-active control (0.5 ml)  
 Placebo-Md = Non-active control (0.15 ml)  
 Placebo-Hd = Non-active control (0.5 ml)

N = total number of subjects with available results  
 n/% = number / percentage of subjects with results outside of the interval  
 range = minimum-maximum for age and intervals

Please note - On Day 3 and Day 33, a visit may take place at the investigators clinical facility or the investigator/clinical staff may call the subjects' parent(s)/LAR(s), as appropriate to the circumstances in the judgment of the investigator

**Template 10 Study Population**

	<Each group> N=XXXX	<Each group> N=XXXX	Total N=XXXX
Number of subjects			
Planned, N	xxx	xxx	xxx
Randomised, N <cohort name>	xxx	xxx	xxx
Completed, n (%)	xxx (xx.x)	xxx (xx.x)	xxx (xx.x)
<Unknown>	xxx	xxx	xxx
Demographics			
N <cohort name>	xxx	xxx	xxx
Females:Males	xxx:xxx	xxx:xxx	xxx:xxx
Mean Age, <unit> (SD)	xxx.x (xxx.x)	xxx.x (xxx.x)	xxx.x (xxx.x)
Median Age, <unit> (minimum, maximum)	xxx (xxx,xxx)	xxx (xxx,xxx)	xxx (xxx,xxx)
<MOST FREQUENT CATEGORY OF RACE>	xxx (xx.x)	xxx (xx.x)	xxx (xx.x)
<SECOND MOST FREQUENT CATEGORY OF RACE>	xxx (xx.x)	xxx (xx.x)	xxx (xx.x)
<THIRD MOST FREQUENT CATEGORY OF RACE>	xxx (xx.x)	xxx (xx.x)	xxx (xx.x)

**<each group>:**

RSV-Ld = Low dose ChAd155-RSV vaccine (5 x 10^9 vp)  
 RSV-Md = Middle dose ChAd155-RSV vaccine (1.5 x 10^10 vp)  
 RSV-Hd = High dose ChAd155-RSV vaccine (5 x 10^10 vp)  
 Placebo-Ld = Non-active control (0.5 ml)  
 Placebo-Md = Non-active control (0.15 ml)  
 Placebo-Hd = Non-active control (0.5 ml)  
 N = Total number of subjects  
 SD = Standard deviation

**Template 11 Number of enrolled subjects by country**

	<each group> N =	Total N =
Characteristics	n	n
Country		

**<each group>:**

- RSV-Ld = Low dose ChAd155-RSV vaccine (5 x 10^9 vp)
- RSV-Md = Middle dose ChAd155-RSV vaccine (1.5 x 10^10 vp)
- RSV-Hd = High dose ChAd155-RSV vaccine (5 x 10^10 vp)
- Placebo-Ld = Non-active control (0.5 ml)
- Placebo-Md = Non-active control (0.15 ml)
- Placebo-Hd = Non-active control (0.5 ml)

N = Number of enrolled subjects

n= number of enrolled subjects included in each group or in total for a given country or for all countries

**Template 12 Number of enrolled subjects by age category**

		<each group> N =	Total N =
Characteristics	Categories	n	n
Age category	1=Infants and toddlers (28 days-23 month)		
	Missing		

**<each group>:**

- RSV-Ld = Low dose ChAd155-RSV vaccine (5 x 10^9 vp)
- RSV-Md = Middle dose ChAd155-RSV vaccine (1.5 x 10^10 vp)
- RSV-Hd = High dose ChAd155-RSV vaccine (5 x 10^10 vp)
- Placebo-Ld = Non-active control (0.5 ml)
- Placebo-Md = Non-active control (0.15 ml)
- Placebo-Hd = Non-active control (0.5 ml)

N = Number of enrolled subjects

n= number of enrolled subjects included in each group or in total for a given age category or for all age categories

Missing = age at dose 1 unknown

**Template 13 Minimum and maximum activity dates <Exposed set>**

		<each group>	<each group>	Overall
Visit Description	Parameter	Date	Date	Date
<each inform consent>	Minimum			
	Maximum			
[Randomisation]	Minimum			
	Maximum			
<each visit>	Minimum			
	Maximum			

**<each group>:**

- RSV-Ld = Low dose ChAd155-RSV vaccine (5 x 10^9 vp)
- RSV-Md = Middle dose ChAd155-RSV vaccine (1.5 x 10^10 vp)
- RSV-Hd = High dose ChAd155-RSV vaccine (5 x 10^10 vp)
- Placebo-Ld = Non-active control (0.5 ml)
- Placebo-Md = Non-active control (0.15 ml)
- Placebo-Hd = Non-active control (0.5 ml)

**Template 14 Exposure to study vaccines <Exposed Set>**

	<Each group> N=XXXX		<Each group> N=XXXX		Total N=XXXX	
	n	%	n	%	n	%
Number of subjects receiving						
Exactly 1 Dose						
Exactly 2 Doses						
...						
At least 1 Dose						
Total number of doses administered during the study						

RSV-Ld = Low dose ChAd155-RSV vaccine (5 x 10^9 vp)  
 RSV-Md = Middle dose ChAd155-RSV vaccine (1.5 x 10^10 vp)  
 RSV-Hd = High dose ChAd155-RSV vaccine (5 x 10^10 vp)  
 Placebo-Ld = Non-active control (0.5 ml)  
 Placebo-Md = Non-active control (0.15 ml)  
 Placebo-Hd = Non-active control (0.5 ml)  
 N = number of subjects in each group or in total included in the considered cohort  
 n = number of subjects/doses in the given category  
 % = percentage of subjects in the given category

**Template 15 Compliance in completing solicited symptoms information <Exposed Set>**

DOSE	Symptom information	<each group>			<each group>		
		N	n	Compliance (%)	N	n	Compliance (%)
DOSE <each dose number>	General SS						
	Local SS						
TOTAL	General SS						
	Local SS						

RSV-Ld = Low dose ChAd155-RSV vaccine (5 x 10^9 vp)  
 RSV-Md = Middle dose ChAd155-RSV vaccine (1.5 x 10^10 vp)  
 RSV-Hd = High dose ChAd155-RSV vaccine (5 x 10^10 vp)  
 Placebo-Ld = Non-active control (0.5 ml)  
 Placebo-Md = Non-active control (0.15 ml)  
 Placebo-Hd = Non-active control (0.5 ml)  
 N=Number of administered doses  
 n = number of doses with SS returned  
 General SS = Symptom screens used for the collection of general solicited AEs  
 Local SS = Symptom screens used for the collection of local solicited AEs  
 Compliance (%) = (n / N) X 100

**Template 16 Incidence and nature of symptoms (solicited and unsolicited) reported during the 7-day post-vaccination period (Days 1-7) following each dose and overall <Exposed Set>**

		<Each group>					<Each group>					Local symptoms				
					95% CI					95% CI					95% CI	
Dose	Symptoms	N	n	%	LL	UL	N	n	%	LL	UL	N	n	%	LL	UL
Dose 1	Any symptom															
	General symptoms															
	Local symptoms															
Dose 2	Any symptom															
	General symptoms															
	Local symptoms															
Overall/dose	Any symptom															
	General symptoms															
	Local symptoms															
Overall/subject	Any symptom															
	General symptoms															
	Local symptoms															

RSV-Ld = Low dose ChAd155-RSV vaccine ( $5 \times 10^9$  vp)  
 RSV-Md = Middle dose ChAd155-RSV vaccine ( $1.5 \times 10^{10}$  vp)  
 RSV-Hd = High dose ChAd155-RSV vaccine ( $5 \times 10^{10}$  vp)  
 Placebo-Ld = Non-active control (0.5 ml)  
 Placebo-Md = Non-active control (0.15 ml)  
 Placebo-Hd = Non-active control (0.5 ml)

For each dose:

N = number of subjects with the corresponding documented dose

n/% = number/percentage of subjects presenting at least one type of symptom following the corresponding dose

For overall/dose:

N = number of documented dose

n/% = number/percentage of doses followed by at least one type of symptom

For overall/subject:

N = number of documented dose

n/% = number/percentage of subjects presenting at least one type of symptom

95% CI = exact 95% confidence interval, LL = Lower Limit, UL = Upper Limit

**Template 17 Incidence of solicited local symptoms reported during the 7-day (Days 1-7) post-vaccination period following each dose and overall <Exposed Set>**

			<each group>				
					95 % CI		
Dose	Symptom	Type	N	n	%	LL	UL
DOSE 1	Pain	All					
		≥ Grade 2					
		Grade 3					
		Medical advice					
	Redness (mm)	All					
		≥ 5					
		>20					
		Medical advice					
	Swelling (mm)	All					
		≥ 5					
		>20					
		Medical advice					
DOSE 2	Pain	...					
	Redness (mm)	...					
	Swelling (mm)	...					
OVERALL/DOSE	Pain	...					
	Redness (mm)	...					
	Swelling (mm)	...					
OVERALL/SUBJECT	Pain	...					
	Redness (mm)	...					
	Swelling (mm)	...					

**<each group>:**

- RSV-Ld = Low dose ChAd155-RSV vaccine (5 x 10^9 vp)
- RSV-Md = Middle dose ChAd155-RSV vaccine (1.5 x 10^10 vp)
- RSV-Hd = High dose ChAd155-RSV vaccine (5 x 10^10 vp)
- Placebo-Ld = Non-active control (0.5 ml)
- Placebo-Md = Non-active control (0.15 ml)
- Placebo-Hd = Non-active control (0.5 ml)

For each dose:

- N = number of subjects with the corresponding documented dose
- n/% = number/percentage of subjects reporting the type of symptom at least once following the corresponding dose

For Overall/dose:

- N = number of documented dose
- n/% = number/percentage of doses followed by at least one type of symptom

For Overall/subject:

- N = number of subjects with at least one documented dose
- n/% = number/percentage of subjects reporting the type of symptom at least once
- 95%CI= Exact 95% confidence interval; LL = lower limit, UL = upper limit
- The maximum intensity of local injection site redness/swelling was coded as follows:
- 1: > 0.1 mm to < 5 mm
- 2: ≥ 5 mm to ≤ 20 mm
- 3: > 20 mm

**Template 18 Incidence of solicited local symptoms reported during the 7-day (Days 1-7) post-vaccination period following each dose and overall by maximum grading <Exposed Set>**

Dose	Symptom	Type	<each group>				
			N	n	%	LL	UL
DOSE 1	Pain	All					
		Grade 1					
		Grade 2					
		Grade 3					
		Medical advice					
	Redness (mm)	All					
		≥0.1 - <5.0					
		≥5.0 - ≤20.0					
		>20					
		Medical advice					
	Swelling (mm)	All					
		≥0.1 - <5.0					
		≥5.0 - ≤20.0					
		>20					
		Medical advice					
DOSE 2	Pain	All					
		Grade 1					
		Grade 2					
		Grade 3					
		Medical advice					
	Redness (mm)	All					
		≥0.1 - <5.0					
		≥5.0 - ≤20.0					
		>20					
		Medical advice					
	Swelling (mm)	All					
		≥0.1 - <5.0					
		≥5.0 - ≤20.0					
		>20					
		Medical advice					
OVERALL/DOSE	Pain	All					
		Grade 1					
		Grade 2					
		Grade 3					
		Medical advice					
	Redness (mm)	All					
		≥0.1 - <5.0					
		≥5.0 - ≤20.0					
		>20					
		Medical advice					
	Swelling (mm)	All					
		≥0.1 - <5.0					
		≥5.0 - ≤20.0					
		>20					
		Medical advice					

Dose	Symptom	Type	<each group>			
			N	n	%	95 % CI LL UL
OVERALL/SUBJECT	Pain	All				
		Grade 1				
		Grade 2				
		Grade 3				
		Medical advice				
	Redness (mm)	All				
		≥0.1 - <5.0				
		≥5.0 - ≤20.0				
		>20				
		Medical advice				
	Swelling (mm)	All				
		≥0.1 - <5.0				
		≥5.0 - ≤20.0				
		>20				
		Medical advice				

RSV-Ld = Low dose ChAd155-RSV vaccine (5 x 10^9 vp)  
 RSV-Md = Middle dose ChAd155-RSV vaccine (1.5 x 10^10 vp)  
 RSV-Hd = High dose ChAd155-RSV vaccine (5 x 10^10 vp)  
 Placebo-Ld = Non-active control (0.5 ml)  
 Placebo-Md = Non-active control (0.15 ml)  
 Placebo-Hd = Non-active control (0.5 ml)

For each dose:

N = number of subjects with the corresponding documented dose  
 n/% = number/percentage of subjects reporting the type of symptoms as maximum intensity during the follow-up period

For Overall/dose:

N = number of documented dose  
 n/% = number/percentage of doses followed by the type of symptom as maximum intensity during the follow-up period

For Overall/subject:

N = number of documented dose  
 n/% = number/percentage of subjects reporting the type of symptom as maximum intensity during the follow-up period  
 CI = Exact 95% confidence interval; LL = lower limit, UL = upper limit

The maximum intensity of local injection site redness/swelling was coded as follows:

- 1: > 0.1 mm to < 5 mm
- 2: ≥ 5 mm to ≤ 20 mm
- 3: > 20 mm

**Template 19 Incidence of solicited general symptoms reported during the 7-day (Days 1-7) post-vaccination period following each dose and overall <Exposed Set>**

			<each group>				
Dose	Symptom	Type	N	n	%	95 % CI	
						LL	UL
DOSE 1	Drowsiness	All					
		≥ Grade 2					
		Grade 3					
		Related					
		≥ Grade 2*Related					
		Grade 3*Related					
		Medical advice					
	Irritability/Fussiness	All					
		≥ Grade 2					
		Grade 3					
		Related					
		≥ Grade 2*Related					
		Grade 3*Related					
		Medical advice					
	Loss of appetite	All					
		≥ Grade 2					
		Grade 3					
		Related					
		≥ Grade 2*Related					
		Grade 3*Related					
Medical advice							
Fever (Axillary) (°C)	All (≥37.5)						
	>37.5						
	>38.0						
	>38.5						
	>39.0						
	>39.5						
	Related						
	>38.5*Related						
	>39.5*Related						
	Medical advice						
DOSE 2	Drowsiness	...					
	Irritability/Fussiness	...					
	Loss of appetite	...					
	Fever (Axillary) (°C)	...					
OVERALL/DOSE	Drowsiness	...					
	Irritability/Fussiness	...					
	Loss of appetite	...					
	Fever (Axillary) (°C)	...					
OVERALL/SUBJECT	Drowsiness	...					
	Irritability/Fussiness	...					
	Loss of appetite	...					
	Fever (Axillary) (°C)	...					

